2.7 Exploratory Outcome Measures

- 1. Gut biopsy tissue and/or systemic biomarkers, which may include but not limited to:
 - GSK1070806 and IL-18
 - Inflammatory biomarkers such as but not limited to, IP10, IFN-γ, CRP, IL-6
 - Composition of immune cell populations
 - Gene expression profiles by transcriptomic analysis
- 2. Proportion of patients in endoscopic response by SES-CD \geq 50% reduction post baseline.
- 3. Genetic variations in host deoxyribonucleic acid (DNA) from blood will be analysed to determine their relationship with response to treatment with GSK1070806 and related diseases

3. TRIAL DESIGN

3.1 Discussion of Design

The proposed study will be a randomised, double blind, placebo-controlled trial to investigate the safety, tolerability, clinical activity, pharmacokinetics and pharmacodynamics of single intravenous infusion (one dose on Day 1) of GSK1070806 or placebo, in patients with active, moderate to severe CD. The primary objective of the study is to assess the safety and tolerability of a single dose IV administration of GSK1070806. A secondary objective will be to evaluate the effect of GSK1070806 in change of CDAI over time. Further secondary endpoints will include assessment of endoscopic response in patients at week 12. (Other secondary endpoints are detailed in Section 2.3).

21 patients will be recruited with randomisation of 2:1 active drug to placebo in multiple centres in the UK.

An initial screening shall take place to identify patients diagnosed with CD for at least 3 months prior to screening and colonoscopic confirmation of active mucosal inflammation (SES-CD excluding narrowed component \geq 6; or in patients with isolated ileal disease \geq 4).

Patients who do not have colonoscopically demonstrated mucosal inflammation will be excluded even if they have MRI evidence of CD more proximally in the small intestine. Colonoscopic SES-CD criteria has to be fulfilled within 28 days prior to dosing.

The induction of clinical activity will be assessed at week 12 by CDAI score, average clinical SF and/or AP scores as well as by colonoscopic assessment of baseline photographic images and/or video recordings and week 12 photographic images and/or video recordings.

The first 5 patients randomised into the trial will be dosed at least 3 days apart. At the interim analysis time point, a safety decision will be taken on the subsequent recruitment and patient spacing out strategy.

Protocol waivers or exemptions are not allowed. Therefore, adherence to the trial design requirements, including those specified in the Schedule of Events Table, are essential.

4. ELIGIBILITY

4.1 Inclusion Criteria

A patient will be eligible for inclusion in this study only if all of the following criteria apply:

- 1. Written informed consent prior to any of the screening procedures including discontinuation of prohibited medications. (see Section 7.11 for additional information)
- 2. Patients must have been diagnosed with Crohn's disease at least 3 months prior to Screening Visit 1
- 3. Patients are required to have endoscopic evidence of active Crohn's disease at Baseline defined by endoscopic appearance: SES-CD excluding the narrowed component of \geq 6 (or \geq 4 for patients with isolated ileal disease).
- 4. AST and ALT \leq 2xULN; alkaline phosphatase and bilirubin \leq 1.5xULN (isolated bilirubin >1.5xULN is acceptable if bilirubin is fractionated and direct bilirubin <35%)
- 5. Male or female participants aged \geq 16 years (up to 80 years)

Male participants:

6. A male participant must agree to use contraception as detailed in Appendix 5 of this protocol for at least 180 days post-dose of study medication and refrain from donating sperm during this period.

Female participants:

- 7. If the patient is breastfeeding, she must agree to stop breastfeeding once randomised into the trial. ¹
- 8. A patient is eligible to participate if she is not pregnant.
- 9. A woman of childbearing potential (WOCBP) is eligible only if she meets at least one of the following conditions:
 - Females on HRT and whose menopausal status is in doubt will be required to use one of the non-hormonal highly effective contraception methods if they wish to continue their HRT during the trial. Otherwise, they must discontinue HRT to allow confirmation of postmenopausal status before trial enrolment.
 - Agrees to follow the contraceptive guidance in Appendix 5 for at least 180 days post-dose of trial medication. If a hormonal method of birth control is selected from the list in Appendix 5 then patients must have been using these methods at least 1 month prior to GSK1070806 administration, or be abstinent, or utilise a condom as a method of contraception until the selected hormonal method has been in place for the 28 day period.
- 10. A woman who is not of childbearing potential is eligible only if she meets at least one of the following conditions:
 - i. Premenopausal female with documented hysterectomy
 - ii Premenopausal female with documented bilateral salpingectomy or oophorectomy
 - iii. Postmenopausal female defined as no menses for 12 months without an alternative medical cause.
 A high follicle stimulating hormone (FSH) level in the postmenopausal range may be used to confirm a postmenopausal state in women not using hormonal contraception or hormonal replacement

¹ A female patient who is breastfeeding may be screened. If randomised into the trial, this patient must agree to stop breastfeeding. Patients who are screened but ineligible can continue breastfeeding.

therapy (HRT). However, in the absence of 12 months of amenorrhea, a single FSH measurement is insufficient.

Note: Documentation can come from the site personnel's review of participant's medical records, medical examination, or medical history assessment.

The Investigator is responsible for ensuring that participants understand how to properly use the indicated methods of contraception by providing counsel directly or by referring participants to health care professionals with expertise in this area.

4.2 Exclusion Criteria

A participant will not be eligible for inclusion in this trial if any of the following criteria apply:

1. Diagnosis of ulcerative or indeterminate colitis

Crohn's Disease complications:

- 2. Evidence of an infected abscess by MRI or other examinations
- 3. Bowel surgery other than appendectomy within 12 weeks prior to screen and/or has planned surgery or deemed likely to need surgery for CD during the trial period
- 4. Participants with ileostomies, colostomies or rectal pouches
- 5. Participants with a bowel stricture that is fixed
- 6. Participants with evidence of short bowel syndrome
- 7. Participants requiring enteral or parenteral feeding
- 8. Deep penetrating ulcers at endoscopy thought to be at risk for perforation

Viral and bacterial infections:

- Presence of Hepatitis B surface antigen (HBsAg), (confirmed by Hepatitis B surface antigen test within 12 months of randomisation) core antigen (HBcAg) or surface antibody (HBsAb), positive Hepatitis C (qualitative enzyme immunoassay) test result
- 10. Known varicella, herpes zoster, or other severe viral infection within 6 weeks of randomisation
- 11. The participant has a history of tuberculosis (TB) disease or latent TB infection, in the absence of documented adequate therapy for same.
- 12. Positive screening test for TB (including T-SPOT.TB TB test), unless respiratory review confirms false positive test results
- 13. History of uncontrolled bacterial or fungal infection requiring intravenous antibiotics
- 14. Positive immunoassay for *Clostridium difficile* toxin and other enteric pathogens

Other exclusion criteria:

- 15. Cardiology assessment/co-morbidity defined as:
- i. QTc >450 msec (480msec for those with Bundle Branch Block) and/or
- ii. either QTcb or QTcf, machine or manual overread, males or females. The QT correction formula used to determine exclusion and discontinuation should be the same throughout the trial and/or
- iii. based on single QTc value (average of triplicate readings) of ECG obtained over a brief recording period
- 16. The participant has congenital or acquired immunodeficiency, or a history of chronic or recurrent opportunistic infections
- 17. The participant has current evidence of, or has been treated for a malignancy within the past five years (other than localised basal cell, squamous cell skin cancer, cervical dysplasia, or cancer in situ that has been resected)
- 18. Use of any investigational drug within 30 days prior to screening, 5 half-lives or twice the duration of the biological effect of the investigational product (whichever is longer)
- 19. Participant has received live, attenuated or recombinant vaccine(s) within 2 months of randomisation or will require vaccination within 3 months of trial drug infusion
- 20. Any patients that are receiving medication(s) detailed in Section 7.11.2 of the trial protocol, will not be eligible for randomisation into the trial

5. SCREENING AND CONSENT

5.1 Informed Consent

It is the responsibility of the Principal Investigator (PI) or Co-investigators (detailed in the site delegation log) to obtain written informed consent for each patient prior to performing any trial related procedure. A Patient Information Sheet (PIS) is provided to facilitate this process. Investigators must ensure that they adequately explain the aim, trial treatment, anticipated benefits and potential hazards of taking part in the trial to the patient. The Investigator should also stress that the patient is completely free to refuse to take part or withdraw from the trial at any time without any detrimental effect on their standard care. The patient should be given ample time (e.g. 24 hrs) to read the PIS and to discuss their participation with others outside of the site research team. The patient must be given an opportunity to ask questions which should be answered to their satisfaction. The right of the patient to refuse to participate in the trial without giving a reason must be respected.

If the patient expresses an interest in participating in the trial they should be asked to sign and date the latest version of the Informed Consent Form (ICF). The PI or Co-investigator (detailed in the site delegation log) must then sign and date the form. A copy of the ICF should be given to the patient, a copy should be filed in the hospital notes, and the original placed in the Investigator Site File (ISF). Once the patient is entered into the trial the patient's trial number should be entered on the ICF maintained in the ISF. In addition, if the patient has given explicit consent a copy of the signed Informed Consent Form must be sent in the post to the Trials Office for review.

Details of the informed consent discussions should be recorded in the patient's medical notes, this should include date of, and information regarding, the initial discussion, the date consent was given, with the name of the trial and the version number of the PIS and ICF. Throughout the trial the patient should have the opportunity to ask questions about the trial and any new information that may be relevant to the patient's continued participation should be shared with them in a timely manner. On occasion it may be necessary to reconsent the patient in which case the process above should be followed and the patient's right to withdraw from the trial respected.

Electronic copies of the PIS and ICF are available from the CDAID Trials Office and should be printed or photocopied onto the headed paper of the local institution.

Details of all patients approached about the trial should be recorded on the Patient Screening/Enrolment Log and with the patient's prior consent their General Practitioner (GP) should also be informed that they are taking part in the trial. A GP Letter is provided electronically for this purpose.

5.1.1 Pharmacogenomics collection consent

The trial includes the collection of a genetic blood sample as this sample will be used to analyse the patients DNA. This sample will be collected using a separate PIS (supplementary sheet) and ICF, in addition to the main PIS and ICF.

Patients can be provided with the information at any time after they have indicated that they would like to take part in the trial (ideally as part of the initial consent process). As this component of the trial is **OPTIONAL**, an individual patients decision on whether he/she would like to participate/provide an additional blood sample for pharmacogenomics analysis will not affect his/her ability to participate in the main trial.

Details of the initial and subsequent pharmacogenomics sample collection consent discussions should be recorded in the patient's medical notes, this should include date of, and information regarding, the initial discussion, the date consent was given, with the name of the trial and the version number of the pharmacogenomics PIS and ICF.

5.2 Screening – assessments and procedures

Prior to the formal screening process, patients will be required to provide written informed consent BEFORE any trial related procedure can be performed, as detailed in Section 5.1. It is anticipated that the majority of the screening process (except baseline colonoscopy procedure) will be completed at the same visit (i.e. all blood tests performed on the same day).

Each patient who has consented, and enters the screening process, will be allocated a screening number. Please use this number in any correspondence with the CDAID Trial Office. If the patient is eligible for the trial, the screening number should be completed on the Randomisation Form. A trial number will be allocated once the patient is randomised.

The screening process consists of two visits which are detailed below:

5.2.1 Screening Visit 1 (within 4 weeks of Randomisation)

- Informed Consent
- Demographic (age , gender, ethnicity)
- Medical and Crohn's history including any current symptoms any pre-existing conditions
- Evaluation of Inclusion / Exclusion Criteria
- Clinical assessment
- Vital signs (heart rate, blood pressure, body temperature (°C), respiratory rate, (all taken in supine position) weight (kg), height (cm))
- Physical exam to be performed by clinician
- Serology screening
- Clostridium Difficile Testing
- Pregnancy test¹ (for female's patients of childbearing potential only)
- 12-lead electrocardiogram (ECG)
- TB screening T-SPOT.TB test (see Appendix 4 T-Spot.TB)
- Biochemistry bloods (see 7.8.1)
- Haematology bloods (see 7.8.1)
- Endoscopy with Biopsy^{2, 3} with photographic images and/or video recordings
- Blood sample (serum) for additional research
- Adverse Event/SAE reporting
- Record of patient concomitant medication (only record con-meds that are currently being taken by the patient)
- CDAI assessment
- Patient Daily Diary

¹ To be performed within 28 days of expected day 1 of treatment (both urine or serum pregnancy tests are acceptable)

² To include biopsy collection (see Section 7.9)

³ Can be performed at any time point within the screening period

5.2.2 Screening Visit 2 (within 1 week of Visit 3)

- Clinical assessment
- Vital signs (heart rate, blood pressure, temperature, respiratory rate)
- Physical exam to be performed by clinician
- Influenza Risk Screening (within 7 days of treatment)
- Biochemistry bloods (see 7.8.1)

- Haematology bloods (see 7.8.1)
- Endoscopy with Biopsy^{1, 2} with photographic images and/or video recordings
- CDAI assessment
- Patient Daily Diary
- Adverse event data collection(including current symptom and any conditions since Visit 1
- Record of patient concomitant medication
- Evaluation of the inclusion/exclusion criteria
- Faecal calprotectin (patient stool sample)

N.B.: After screening visit 2 randomisation can be undertaken – see Section 6.1)

¹To include biopsy collection (see Section 7.9)

² Can be performed at any time point within the screening period

6. TRIAL ENTRY

6.1 Randomisation

After the results of the screening process (Visit 2) are available, and the patient is eligible, they can be randomised with the CDAID Trials Office and given a unique trial number. The following will be verified by the local site PI and/or Co-Investigators before randomising the patient onto the trial:

- Confirmation of all the inclusion criteria at the time of Randomisation (Visit 2)
- Review of all the exclusion criteria- at the time of Randomisation (Visit 2)
- Completion of Eligibility Form
- Completion of Randomisation Form

All the above must be completed before proceeding onto patient randomisation.

All patients must be randomised with the CRCTU at the University of Birmingham and their trial number will provided at the end of the Randomisation process.

Randomisation of patients can be achieved by logging on to:

https://www.cancertrials.bham.ac.uk

At this time point, patients will be allocated a unique trial number to preserve patient confidentiality. The schedule for investigations and follow up visits is summarised in Section 7.7 and 7.13

Emergency randomisation is not available in the CDAID trial.

6.1.1 Protocol waivers or exemptions

Protocol waivers or exemptions are not allowed with the exception of immediate safety concerns. Therefore, adherence to the trial design requirements, including those specified in the schedule of events table, the trial protocol are essential and required for trial conduct. Any deviation from protocol procedures should be documented as a protocol deviation on the appropriate case report form (CRF).
7. TREATMENT DETAILS

7.1 Investigational Medicinal Product Preparation

7.1.1 Experimental group

Product name:	GSK1070806
Active Substance	GSK1070806 – Humanised IgG1 antibody
Dosage form:	100 mg/mL injectable solution
Unit dose strength(s)/Dosage level(s):	Single dose of 10 mg/kg
Route of Administration	IV infusion
Dosing instructions:	Dilute into 100 mL sterile IV infusion bag 0.9% Sodium Chloride (details see Pharmacy Manual)

7.1.2 Placebo Controlled group

Product name:	Sodium chloride (0.9%)
Active Substance	Not applicable
Dosage form:	injectable solution
Unit dose	100mls
strength(s)/Dosage level(s):	
Route of	IV infusion
Administration	
Dosing instructions:	100 mL sterile IV infusion bag 0.9% Sodium Chloride
	(details see Pharmacy Manual)

7.2 Dosage Form and Composition

The dosage form and composition of GSK 1070806 is detailed in the Pharmacy Manual.

7.3 Instructions for handling and preparation of Investigational Medicinal Product

A description of the methods and materials required for preparation of GSK1070806 is detailed in the Pharmacy Manual. Trial treatment must be dispensed or administered according to procedures described herein and in the Pharmacy Manual.

Only subjects enrolled in the trial may receive trial treatment. Only authorised site staff may supply or administer trial treatment. All trial treatment must be stored in a secure area with access limited to the Investigator and authorised site staff.

The Investigator is responsible for trial treatment, accountability, reconciliation, and record maintenance. The Investigator or the head of the medical institution (where applicable), or designated site staff (e.g., storage manager, where applicable) must maintain trial treatment accountability records throughout the course of the trial. The responsible person(s) will document the amount of trial treatment received from GSK (complete all appropriate procedures relating to the condition of the IMP/trial documentation; temperature logs etc.) and the amount administered to subjects. In addition to any excess stock disposed of in accordance with the local standard operating procedure for IMP disposal. The required accountability unit for this trial will be the vial. Discrepancies are to be reconciled or resolved. Procedures for final disposal of unused trial treatment are listed in the Pharmacy Manual.

Investigational product is not expected to pose significant occupational safety risk to site staff under normal conditions of use and administration. However, precautions are to be taken to avoid direct skin contact, eye contact, and generating aerosols or mists. In the case of unintentional occupational exposure notify the monitor, medical monitor and/or trial manager. A Material Safety Data Sheet describing occupational hazards and recommended handling precautions either will be provided to the Investigator, where this is required by local laws, or is available upon request from GSK/ Sponsor.

7.4 Packaging and Labelling

The contents of the label will be in accordance with all applicable regulatory requirements.

7.5 Trial Treatment

This clinical trial is a randomised, double-blind, placebo- controlled trial therefore all patients randomised will receive one of the following groups (see Table 1)

Table 1: Treatment groups

Group 1	Control group: treatment with single infusion of inactive treatment (GSK1070806 Placebo)
Group 2	Experimental group: treatment with single infusion (10mg/kg) of active treatment (GSK1070806)

The infusion pump speed should be 80ml/per hour for all the patients with total infusion time of an hour.

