7.7 Treatment Schedule

7.7.1 Treatment Visit 3 (Day 1 – Week 1)

- Clinical assessment
- Vital signs (heart rate, blood pressure, oral body temperature (°C), respiratory rate) taken pre-dose, and at 30 minutes interval during infusion period and repeated at 30 minute intervals for a period of 3 hours post infusion (removal of needle). Weight (kg) to be measured pre-infusion only
- Physical exam to be performed by clinician
- Influenza risk screening (prior to treatment)
- Pregnancy test (for female's patients of childbearing potential only)
- 12-lead ECG pre-infusion and 60 mins post infusion
- Biochemistry bloods (see Section 7.8.8)
- Haematology bloods (see Section 7.8.8)
- Blood serum for PK (pre-infusion sample to be taken within 1 hour of start of infusion, end of infusion sample to be taken within 15 minutes of end of infusion, and one sample taken between 4 hours and 8 hours post infusion start, see Figure 3 Pharmacokinetics sample time points)
- Blood serum for PD (pre-infusion only)
- Bloods for FBC, INR, UE, LFT 2hrs post end of infusion period. See Table 3
- CDAI assessment
- Blood serum for Immunogenicity (pre dose) analysis.
- Patient Daily Diary
- GSK1070806 / or Matched Placebo infusion
- Faecal calprotectin (patient stool sample) (if available post infusion or within 24 hours post infusion)
- Adverse Event/SAE reporting
- Record of patient concomitant medication
- Genetics/pharmacogenomics sample for optional genetic research
- Blood sample (serum) for additional research

For infusion reaction management/concomitant medication associated with GSK1070806 see Section 8.1.1.3 and Section 7.11.

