7.7.3 Treatment compliance

GSK1070806 or matched placebo will be prepared by site in accordance with the pharmacy manual. The allocated treatment will be prepared by suitably qualified pharmacy personnel (detailed one the site delegation log) and labelled with the trial specific label in order to maintain the trial blind. Only the site pharmacy personnel will be unblinded to the trial medication. All other trial personnel within the site will be blind to the allocated treatment for each individual patient. The allotted trial medication will subsequently be stored and be administered intravenously (within a given timeframe) to subject as an infusion at the trial site in accordance with the pharmacy manual and local procedures.

The full and accurate record of drug preparation (batch numbers, and time of preparation, dispensing and time of actual administration) will be maintained within the individual site pharmacy file and subsequent treatment compliance. This information will be provided to the Sponsor upon request and some information will be recorded within the case report form. Full drug accountability records and infusion start/stop times, flow rates, reasons for any interruptions in drug delivery will be maintained by the participating site and some of this information will also be recorded within the case report form.

Please refer to the current CDAID Pharmacy Manual for further information.

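### Section 7.5's rate and duration deliver 80 mL, but Section 7.1.2 gives the placebo dose as 100 mL; the volume to be infused in the active arm is not stated

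*Protocol*

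**What the plan says.** Section 7.5 of the protocol gives the administration rule for both groups: "The infusion pump speed should be 80ml/per hour for all the patients with total infusion time of an hour".

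Section 7.1.2 describes the placebo. Its field for unit dose strength and dosage level reads 100 mL, and its dosing instruction names a "100 mL sterile IV infusion bag 0.9% Sodium Chloride", with details left to the Pharmacy Manual.

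Section 7.1.1 describes the active product as a 100 mg/mL solution given once at 10 mg/kg. Its dosing instruction is "Dilute into 100 mL sterile IV infusion bag 0.9% Sodium Chloride (details see Pharmacy Manual". It states neither a final volume nor a volume to be infused.

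Section 7.3 makes both documents binding: "Trial treatment must be dispensed or administered according to procedures described herein and in the Pharmacy Manual". Nowhere does the protocol state a volume of 80 mL, or tell staff to leave or discard part of a bag.

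**The concern.** Rate multiplied by time gives volume, so once Section 7.5 fixes the first two, the third is fixed as well. The result is 80 mL, while the only volume the protocol gives as a dose is 100 mL. A nurse following the placebo entry and Section 7.5 together has to depart from one of the three figures, and Section 6.1.1 asks for deviations from protocol procedures to be documented.

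This is the operative rule for the only dose in the trial. Section 7.6 allows no dose reduction and Section 7.7.6 no further infusion. In the active arm, an instruction to stop at one hour could leave drug in the bag if the dose is spread through 100 mL. Section 1.2.3 explains why the full dose was chosen: the modelling cited there predicts that 10 mg/kg is needed to hold IL-18 suppression in the gut interstitium above 99% for 90 days.

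**Working it through.** **Inputs**
- Rate 80 mL/h and duration 1 h, all patients (Section 7.5).
- Placebo unit dose 100 mL (Section 7.1.2).
- Active dose 10 mg/kg from a 100 mg/mL solution, diluted into a 100 mL bag (Section 7.1.1).
- Assumed, because the protocol does not give them: body weights of 50 to 100 kg, and whether the drug volume replaces saline in the bag or is added to it.

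**Placebo arm**
- Volume delivered = rate × time = 80 mL/h × 1 h = 80 mL.
- Left in a 100 mL bag at one hour = 100 − 80 = 20 mL (20%).
- Time for 100 mL = volume / rate = 100 / 80 = 1.25 h = 75 minutes, which is 15 minutes more than 60 (15 / 60 = 25%).
- The stated one hour is reproduced only with a volume of 80 mL (80 / 80 = 1 h), or with a rate of 100 mL/h (100 / 100 = 1 h).

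**Active arm, conditional on the whole dose being mixed through the bag and the pump being stopped at 60 minutes**
- Drug volume = 10 mg/kg × weight / 100 mg/mL = 0.1 mL/kg, or 5 to 10 mL at 50 to 100 kg.
- If the drug replaces saline, the total is 100 mL: 80 / 100 = 80% is delivered, which is 8.0 mg/kg. The full bag takes 75 minutes.
- If the drug is added to 100 mL, the total is 105 to 110 mL: 80 / 105 = 76% to 80 / 110 = 73% is delivered, or 7.6 to 7.3 mg/kg. The full bag takes 78.8 to 82.5 minutes.
- If the final volume is 80 mL, or the bag is run out, the full 10 mg/kg is given.

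**Does running out a 100 mL bag disturb the Day 1 schedule?** In minutes from the start of infusion:

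| Event (Sections 7.7.1 and 7.10) | Time |
|---|---|
| End of infusion | 75 |
| End-of-infusion PK sample, within 15 minutes | by 90 |
| ECG, 60 minutes after infusion | 135 |
| Bloods, 2 hours after infusion | 195 |
| End of 3-hour observation | 255 |
| Later PK window | 240 to 480 |

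The later PK sample is "one sample taken between 4 hours and 8 hours post infusion start", so its window opens 240 − 75 = 165 minutes after the infusion ends. Every assessment can still be done as written.

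**The case against.** The strongest reply is that 100 mL may describe the bag supplied and not the volume infused. The protocol never uses a term for volume to be infused, both product tables refer to the Pharmacy Manual, and infusing 80 mL from a 100 mL bag would satisfy Section 7.5. This has some force: the conflict depends on how the placebo entry is read. But Section 7.1.2 gives 100 mL twice, once as the bag and once in the dose field, and a dose field ordinarily states what the patient receives. Nor can the manual settle the matter by itself, because Section 7.3 binds sites to the protocol as well. A manual that set 100 mL would conflict with Section 7.5, and one that set 80 mL would leave the dose entry in Section 7.1.2 wrong.

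The second reply is that the firm part has no demonstrated consequence. That stands. The placebo is saline, and the timeline shows no assessment lost if the bag is run out.

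A reader might go further and infer that active patients will be under-dosed. The document does not support that. It requires both that the dose be mixed through the full bag and that staff stop with drug remaining, and no section tells them to do so. Sections 7.1.1 and 7.5 fix 10 mg/kg, and Section 7.7.4 requires a full record if an infusion is stopped.

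A reader might also infer a threat to blinding, with the arms running for visibly different times, given that "Only the site pharmacy personnel will be unblinded to the trial medication". That would need the manual to set different volumes by arm. Nothing suggests this, and Section 7.5 sets one rate and one duration for everyone.

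Finally, a reader might assume that the records would reveal any shortfall. Section 7.7.3 says that "infusion start/stop times, flow rates, reasons for any interruptions in drug delivery will be maintained by the participating site", but it sends only some of this to the case report form. The requirement in Section 7.3 to document "the amount administered to subjects" belongs to drug accountability for product received from the supplier, which is counted by the vial. The protocol therefore does not establish that infused volume is captured.

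**Conclusion.** The point holds as a minor inconsistency. Section 7.5 implies 80 mL and Section 7.1.2 gives 100 mL. The gap is 20 mL, or 15 minutes at the stated rate. It rests on reading the placebo dose entry as the volume to be infused, which is the natural reading though not the only possible one.

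The certain part affects no drug dose. For the active arm, the size of the conditional risk is 20% of the dose (8 instead of 10 mg/kg) if the total is 100 mL, and up to about 27% at 100 kg if the drug is added to a 100 mL bag. Whether it could arise depends on the Pharmacy Manual and cannot be decided from the protocol. Section 1.2.3 gives no model prediction at 8 mg/kg. It puts suppression above 90% at 1 mg/kg, so the pharmacological cost of such a shortfall cannot be sized from this document either. Sample size, power and error rates are untouched.

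**What to change.** In Section 7.5, state one total volume to be infused, the same in both arms, and require that the whole prepared volume is given. Make rate and duration agree with it. Any of these is consistent:
- 100 mL at 100 mL/h over 60 minutes;
- 100 mL at 80 mL/h over 75 minutes;
- 80 mL at 80 mL/h over 60 minutes.

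The choice belongs to the sponsor and pharmacy, who know the prepared volume. If the drug is added to a full bag, the stated volume should allow for it. Then align Sections 7.1.1 and 7.1.2 and the Pharmacy Manual. The cost is one corrected sentence and a check of three matching entries.
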